As noted above, side effects will be assessed in several ways: daily assessments via the sleep diaries and weekly evaluation with a medical symptom checklist (52 symptoms where positive endorsements allow subjects to rate their average severity and number of days affected).

10. Statistical Plan

k. Primary Endpoint

The primary endpoint is total wake time (time spent awake in bed) at the end of post-treatment, as measured via a web based self-report Sleep Diary.

I. Secondary Endpoints

1. Patients treated with CBT-I will have significantly greater improvements in sleep continuity from baseline to post-treatment compared to patients not administered CBT-I.
2. Patients treated with CBT-I in combination with solriamfetol will have significantly greater improvements in sleep continuity from baseline to post-treatment compared to patients treated with CBT-I alone.
3. Exploratory hypotheses: Patients treated with CBT-I in combination with solriamfetol will have significantly greater adherence with sleep restriction (i.e., sleep rescheduling, prescribed time to bed [PTTB]) and on daytime performance measures (e.g., ESS, FSS, etc.) compared to CBT-I alone.

m. Sample Size and Power Determination

To detect a clinically significant difference in self-reported total wake time of 30 minutes between the four treatment groups at the end of post-treatment using an ANOVA test, this study will require 10 subjects per group x 4 groups = 40 treatment completers. These calculations assume a standard deviation in total wake time of 19 minutes, with 80% power to detect the clinically significant change at an alpha level of .05. A total of 60 subjects will be recruited to obtain a sample of 40 subjects that complete the study due to attrition.

n. Statistical Methods

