Primary analyses will be conducted on an intention to treat basis and the trial conducted and reported according to CONSORT guidelines. Variable distributions will be examined to investigate homoscedasticity, outliers and normality, and corrected where appropriate using data transformations. The primary analysis is a 4(condition: +/- solriamfetol and +/- CBT-I) x 2(time: pre- and post-treatment) mixed ANOVA on absolute and percent change in total wake time ([TWT], time spent awake per night). If the interaction between condition and time is significant, Dunnett multiple comparisons will be conducted to further investigate differences in TWT between active treatment conditions versus the control condition to test Hypotheses 1-3. These analyses will be unadjusted in the first instance and then adjusted for covariates (primarily, age and sex).

An interim unadjusted analysis as per above will be conducted after 50% of the target sample have completed post-treatment (i.e., when N=20).

Secondary analyses include examining the interaction between treatment condition and time on other outcomes, including sleep continuity assessed via Sleep Diary (SL, WASO, EMA, TST, SE), insomnia (ISI), daytime sleepiness (ESS and KSS), fatigue (FSS and modified KSS), and daytime function (FOSQ-10, POMS, and PVT). Additionally, compliance to the medication (adherence to daily pill administration, as assessed via blister packs) and to sleep restriction (adherence to prescribed time to bed) will be investigated as covariates.

i. Baseline Data

Baseline and demographic characteristics will be summarized by standard descriptive statistics (including mean and standard deviation for continuous variables such as age and standard percentages for categorical variables such as gender).

ii. Pharmacokinetic Analysis **N/A**

iii. Interim Analysis **N/A**

iv. Safety Analysis

Side effects and adverse events will be assessed in several ways: daily assessments via the sleep diaries, and with a weekly evaluation using a medical symptoms checklist (52 symptoms where positive endorsements allow subjects to rate their average severity and number of days affected),

An adverse event will be defined as 1) any behavioral or health complaint spontaneously reported during the study, 2) an above threshold score on the study clinical assessment instruments (ESS, PHQ-9, or GAD-7), and/or a 20% increase in the medical symptom check list scores (frequency or severity).

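### The Dunnett comparisons are made to wait for a significant omnibus interaction they do not need; dropping that condition gains up to about 6 points of any-arm power across the 30-minute patterns tried with SD 19

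*Combined protocol and SAP*

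**What the plan says.** Section 10.n (Statistical Methods) names as the primary analysis a four-condition "x 2(time: pre- and post-treatment) mixed ANOVA on absolute and percent change in total wake time". The comparisons between arms come second and are conditional: "If the interaction between condition and time is significant, Dunnett multiple comparisons will be conducted to further investigate differences in TWT", the comparisons being "between active treatment conditions versus the control condition to test Hypotheses 1-3". No reason is given for the condition, and no route is given for testing the hypotheses if the interaction is not significant.

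Section 10.m (Sample Size and Power Determination) sizes the trial on an ANOVA: "To detect a clinically significant difference in self-reported total wake time of 30 minutes between the four treatment groups". It continues: "These calculations assume a standard deviation in total wake time of 19 minutes". It sets power at 80% and alpha at .05, and concludes that "this study will require 10 subjects per group x 4 groups = 40 treatment completers". It does not say how the four means are arranged within the 30 minutes. Section 3 expects both treatments to work, possibly additively.

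Section 10.n also plans an interim analysis of the same kind at N=20, although item iii of that section marks interim analysis as not applicable.

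**The concern.** An omnibus test is sometimes placed before pairwise comparisons to protect procedures that do not control multiplicity themselves. Dunnett's procedure is not one of these. Its critical value comes from the joint distribution of the three active-versus-control statistics, so it holds the family-wise error at 5% without a preliminary F test. Requiring a significant 3-df interaction as well makes the two-step procedure conservative. An arm can clear the Dunnett threshold while the omnibus test misses .05, and the plan then gives no formal test of that arm. With 10 completers per arm, power should not be given up without a reason.

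**Working it through.** **Inputs.** From 10.m: 10 per arm, four arms, a 30-minute difference, SD 19 minutes, alpha .05, power 80%. From 10.n: the interaction test as precondition and three comparisons with control. Assumed: the pattern of means, a two-sided Dunnett test, and 19 minutes as the SD of change.

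**Step 1: the test.** With two time points, the condition-by-time interaction is the same as a one-way ANOVA on pre-post change. The degrees of freedom are 3 and 4 × (10 − 1) = 36, and the F critical value is 2.866.

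**Step 2: reproduce the stated power.** Place two means at the ends of the 30-minute range and two at the midpoint. The noncentrality is n × Σ(deviation²)/SD² = 10 × (15² + 0 + 0 + 15²)/19² = 4500/361 = 12.47. Power is 81.1% at n = 10 and 75.8% at n = 9, so 10 is the smallest number per arm that reaches 80%. With control at one end, this is 0/15/15/30 (control, solriamfetol, CBT-I, combination), which also fits the additive expectation.

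**Step 3: cost of the precondition.** The two-sided Dunnett critical value for three comparisons and 36 df is 2.452. Simulation (1,000,000 trials per pattern, Monte Carlo error at most 0.05 points) compared P(Dunnett rejects) with P(Dunnett rejects and F > 2.866). Losses are taken from unrounded values.

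| Reduction in minutes | Omnibus power | Any arm, no precondition | Any arm, with precondition | Loss (points) |
|---|---|---|---|---|
| 0/15/15/30 | 81.1% | 86.6% | 80.2% | 6.4 |
| 0/10/20/30 | 85.4% | 87.6% | 83.3% | 4.3 |
| 0/30/30/30 | 94.5% | 96.7% | 94.5% | 2.2 |
| 0/0/0/30 | 94.5% | 86.2% | 85.5% | 0.8 |
| Control at midpoint, others +15/−15/0 | 81.1% | 49.4% | 48.9% | 0.5 |
| 0/0/30/30 | 98.6% | 94.4% | 94.3% | 0.2 |
| No effect in any arm | 5.0% | 5.0% | 3.2% | 1.8 |

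**Step 4: where the loss falls at 0/15/15/30.** Combination versus control goes from 85.4% to 79.4%. Solriamfetol alone versus control goes from 26.1% to 25.8%, a loss of about 0.2 points before rounding.

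**Step 5: equivalent in patients at 0/15/15/30.** With the precondition, any-arm power is 84.7% at n = 11 and 88.2% at n = 12. Interpolating to 86.6% gives (86.6 − 84.7)/(88.2 − 84.7) = 0.54, so about 11.5 per arm. The precondition costs about 1.5 completers per arm.

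**Step 6: sensitivity to the SD of change.** If 19 minutes is the SD at one time point, the SD of change is 19 × √(2(1 − ρ)), where ρ is the pre-post correlation. Under 0/15/15/30 with 10 per arm:

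- ρ = 0.3: SD 22.5, any-arm power 72.4% without and 63.8% with the precondition, loss 8.7.
- ρ = 0.5: SD 19.0, loss 6.4.
- ρ = 0.7: SD 14.7, 98.1% against 96.4%, loss 1.8.

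If all 60 recruits were analysed (15 per arm) at ρ = 0.5, the loss is 2.2 points.

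**Step 7: what the 5% does not cover.** Suppose the N=20 look (five per arm) and the final analysis are each tested at a full .05. With no effect in any arm, the false-claim rate is about 8.7% without the precondition and 5.7% with it.

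**The case against.** The strongest reply is that the omnibus test is the named primary analysis and the basis of the sample size, and that any-arm power with the precondition is 80.2%, the level promised. That stands. A reader might infer that the precondition leaves the trial underpowered; at the pattern that reproduces the plan's own figure, it does not.

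The second reply is that six points is a selective figure. In part it is. The pattern is inferred, the loss is smaller under every other 30-minute pattern in the table, and it falls mainly on combination versus control. Sections 5.6 and 5.6.2 list drug versus placebo, CBT-I versus no CBT-I, and combination versus CBT-I alone; none of these is combination versus double control. For solriamfetol alone versus control, the Dunnett comparison closest to the hypothesis the study says it is powered for, the loss at 15 minutes is negligible.

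Third, a reader might infer that the precondition does nothing but discard true effects, or that removing it leaves the whole plan at 5%. Neither follows. It also removes false positives (5.0% to 3.2%), though the 5% level does not require this. Dunnett's guarantee does not extend to the interim look or to the use of two outcome scales, and removing the precondition without addressing these raises the overall false-claim rate (Step 7). The precondition was not designed for that purpose and does not bring the two-look rate down to 5%.

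Finally, a reader might infer that a non-significant interaction forbids reporting any arm result. Section 10.n bars only the formal comparisons, and the Publication Plan gives effect-size estimation as the main intent, so estimates would still be relevant.

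**Conclusion.** The concern holds as a point of efficiency. The precondition is unnecessary for 5% control within one Dunnett family and can only lower power. The loss in any-arm power is 6.4 points under 0/15/15/30 with 19 minutes as the SD of change, and between about 0 and 4 points under the other 30-minute patterns tried. The size rests on a pattern of means and a pre-post correlation that the plan does not state; the direction rests on neither. The change is worth making because it is nearly free, but the trial does not fail its stated target without it.

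**What to change.** In 10.n, delete the opening conditional clause of the sentence that introduces the Dunnett comparisons. State that the Dunnett-adjusted comparisons, or whichever planned contrasts are finally named, are carried out and reported with simultaneous 95% confidence intervals whatever the omnibus result. The interaction test can stay in the report alongside them, but not as a condition for them.

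Add that the 5% control applies to one family of three comparisons with control, at one analysis, on one outcome scale. The N=20 look and the pairing of absolute with percent change need their own multiplicity rules. Combination versus CBT-I alone is not a comparison with control, so it lies outside the Dunnett family and needs its own place in the plan. In 10.m, state the assumed pattern of means and whether 19 minutes is the SD of change.

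The cost is a few sentences, with no additional patients or data. Deleting the clause without the statement on multiplicity would be incomplete.

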3.1 Primary Objective(s)

To investigate the effects of solriamfetol on sleep continuity, alone and in combination with CBT-I.

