5.6 Study Endpoints

Primary hypothesis

1. Patients administered solriamfetol will have significantly greater improvements in sleep continuity (total wake time [TWT]) from baseline to post-treatment compared to patients administered placebos. Note: the study is powered for this hypothesis.

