5.6.2 Secondary Study Endpoints

1. Patients treated with CBT-I will have significantly greater improvements in sleep continuity from baseline to post-treatment compared to patients not administered CBT-I.
2. Patients treated with CBT-I in combination with solriamfetol will have significantly greater improvements in sleep continuity from baseline to post-treatment compared to patients treated with CBT-I alone.
3. **Exploratory hypotheses:** Patients treated with CBT-I in combination with solriamfetol will have significantly greater adherence with sleep restriction (i.e., sleep rescheduling, prescribed time to bed [PTTB]) and on daytime performance measures (e.g., ESS, FSS, etc.) compared to CBT-I alone.

i. Primary Safety Endpoints [if applicable]

As noted above, side effects will be assessed in several ways: daily assessments via the sleep diaries, weekly evaluation with a medical symptom checklist (52 symptoms where positive endorsements allow subjects to rate their average severity and number of days affected).

6. Study Population and Duration of Participation

Subjects 25 to 65 years old (inclusive) and who have a stable sleep/wake schedule (no shift work) with a preferred sleep phase between 10:00 PM and 8:00 AM. The recruitment sample will be populated by 40 completed subjects. The study duration will be 12 weeks, with a one-time follow-up at 3 months post-treatment.

a. Inclusion Criteria

Participants will meet the diagnostic criteria for Insomnia Disorder according to Diagnostic and Statistical Manual of Mental Disorders (DSM-5). The complaint of disturbed sleep will meet the following criteria:

- ≥ 30 minutes to fall asleep (SL) and/or ≥ 2 awakenings per night of ≥ 15 minutes duration and/or wake after sleep onset (WASO) time of ≥ 30 minutes where total sleep time (TST) did not exceed 6 hours (unless sleep efficiency [SE] is $\leq 80\%$).
- The problem is present for ≥ 3 nights per week.
- The problem duration exceeds ≥ 6 months.
- The complaint of impaired daytime function must include, although not limited to, the report of daytime fatigue, sleepiness, or both.

Additional inclusion criteria are as follows.

1. Aged 25 to 65 years (inclusive).
2. Have a preferred regular sleep phase between 10:00 PM and 8:00 AM.

b. Exclusion Criteria

Please note that all subjects will have to receive physician assent before being enrolled into the study.

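### No single Dunnett control can test all three hypotheses; with placebo as control, combination versus CBT-I alone has no planned contrast

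*Combined protocol and SAP*

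**What the plan says.** Section 10.n (Statistical Methods) makes the primary analysis a "4(condition: +/- solriamfetol and +/- CBT-I) x 2(time: pre- and post-treatment) mixed ANOVA" on TWT, with condition as one four-level factor. If condition by time is significant, the follow-up is: "Dunnett multiple comparisons will be conducted to further investigate differences in TWT between active treatment conditions versus the control condition to test Hypotheses 1-3". The section does not say which arm is the control. The synopsis lists CBT-I as the reference therapy.

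The hypotheses are spread over two lists, and the numbering restarts between them. Taken in order they are:

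- **H1, solriamfetol** (5.6, primary): patients given solriamfetol will have "significantly greater improvements in sleep continuity (total wake time [TWT]) from baseline to post-treatment compared to patients administered placebos".
- **H2, CBT-I** (5.6.2 and 10.l, item 1): "Patients treated with CBT-I will have significantly greater improvements in sleep continuity from baseline to post-treatment compared to patients not administered CBT-I".
- **H3, combination** (5.6.2 and 10.l, item 2): CBT-I with solriamfetol will show "significantly greater improvements in sleep continuity from baseline to post-treatment compared to patients treated with CBT-I alone".

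The primary objective in 3.1 is: "To investigate the effects of solriamfetol on sleep continuity, alone and in combination with CBT-I".

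On timing, 10.n states: "An interim unadjusted analysis as per above will be conducted after 50% of the target sample have completed post-treatment (i.e., when N=20". Item iii of the same section marks interim analysis as not applicable.

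**The concern.** H3 compares two active arms. A many-to-one procedure contains that comparison only if one of those two arms is the control. H3 asks whether the drug adds anything to CBT-I, which is also the second half of the primary objective. If the contrast is chosen only after unblinded data are seen, the answer is post hoc. H2 has a milder mismatch: its wording pools over solriamfetol, but the plan offers only one pair of arms.

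**Working it through.** **1. The plan's own sample size.** Section 10.m gives a 30-minute difference among four groups, SD 19, alpha .05, 80% power and 10 completers per group. It does not give the pattern of means. Assume the least favourable pattern for a 30-minute range, 0/15/15/30. The noncentrality is n × Σ(mean − grand mean)² / SD² = 10 × (15² + 0 + 0 + 15²) / 19² = 10 × 450 / 361 = 12.47, with 3 and 36 df. Power is 0.811, and 0.758 with 9 per group, so 10 per group is reproduced. This is power for the four-group omnibus test, not for any one hypothesis.

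**2. Which contrasts each control gives.**

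| Hypothesis | Control = placebo, no CBT-I | Control = CBT-I + placebo |
|---|---|---|
| H1 solriamfetol | solriamfetol alone vs placebo alone | that pair is lost |
| H2 CBT-I | CBT-I + placebo vs placebo alone (one pair) | the same pair, reversed |
| H3 combination | **none** | combination vs CBT-I + placebo |

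If Hypotheses 1-3 instead means items 1 to 3 of 5.6.2, item 2 is still the combination hypothesis, so the gap remains. The secondary analyses in 10.n repeat condition by time on other outcomes and add no TWT contrast.

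**3. Power of the available and missing contrasts.** Assumptions: SD 19 applies to change in TWT (10.m states it for TWT itself), 10 per arm, 36 df, two-sided 5%.

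- SE of a pair: 19 × √(2/10) = 8.50 min.
- SE of a pooled contrast, 20 vs 20: 19 × √(1/10) = 6.01 min.
- Critical values: 2.028 for a single test; 2.452 for Dunnett with three comparisons.

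| Contrast | 30 min | 15 min |
|---|---|---|
| Dunnett pair (planned) | 85% | 26% |
| Combination − CBT-I + placebo, unadjusted | 93% | 40% |
| Same, tested at 0.025 | 88% | 30% |
| Pooled CBT-I (or pooled solriamfetol) contrast | 99.8% | 68% |

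The pooled row takes the effect to be the same at both levels of the other factor.

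**4. Combination versus placebo cannot stand in for H3.** With means (placebo / solriamfetol / CBT-I / combination) of 0/30/30/30, the combination does no better than CBT-I alone. Its Dunnett comparison with placebo is still significant in about 85% of simulated trials. The plan does not propose this inference; the figure shows only why that comparison cannot fill the gap.

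**5. What multiplicity control would cost H3.** Simulation, 400,000 trials per pattern, same assumptions. H2 is the pooled CBT-I contrast, and a fixed sequence tests H1, then H2, then H3, each at 0.05.

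| Rule for H3 | 0/0/30/60 | 0/15/30/45 |
|---|---|---|
| Unadjusted | 93% | 40% |
| Tested at 0.025 | 88% | 30% |
| Fixed sequence, H1 pooled | 67% | 38% |
| Fixed sequence, H1 = unadjusted solriamfetol-alone pair | about 5% | about 17% |

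A rough check on the last row: for 0/0/30/60 the H1 pair has no true effect, so it passes 5% of the time, and 0.05 × 0.93 ≈ 0.05. For 0/15/30/45 both pairs have about 40% power, and 0.40 × 0.40 = 0.16. H2 almost always passes under both patterns.

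**The case against.** The best defence concerns H1. A reader might infer that the Dunnett plan fails all three hypotheses, or that H1 is wrongly tested or underpowered. The documents do not support that. Section 3.1 speaks of solriamfetol alone as well as in combination, so solriamfetol alone versus placebo alone is a legitimate simple-effect reading of H1. It is prespecified under the natural choice of control, and its 85% power exceeds the planned 80%. If effects are strongly sub-additive (0/30/30/30), it outperforms the pooled test, 85% to 68%. Pooled or simple is the sponsor's choice, not an error.

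A second defence is that the synopsis names CBT-I as reference therapy, which would make combination versus CBT-I alone a Dunnett contrast. This stands as far as it goes: it would be too strong to say that H3 is untested under every reading. But the wording of 10.n, active conditions against the control, points to the one arm with no active treatment, and the other choice only moves the gap to the solriamfetol pair.

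Third, H3 is secondary, and the Publication Plan says the main purpose is to obtain effect sizes. That lowers the stakes but does not remove the point. Section 10.n commits to testing the hypotheses, and the Publication Plan foresees a report if results are significant with 5 to 8 subjects per condition.

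Finally, a reader might take an unblinded look at N=20 as certain. The section both plans it and marks interim analysis as not applicable, so that cannot be assumed.

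**Conclusion.** The point holds in this form: a Dunnett family with one control cannot test Hypotheses 1-3. On the natural reading the combination hypothesis has no planned contrast, and on the alternative reading solriamfetol alone versus placebo alone has none. The CBT-I hypothesis gets a narrower test than its wording: one pair of 10 vs 10 completers, or 15 vs 15 if all 60 recruited are analysed in equal groups. The H1 pair is valid.

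The logical gap does not depend on any assumed effect or SD. The power figures do: they rest on SD 19 applying to change, 10 per arm and the patterns of means shown. It should be fixed, and the present group size gives the missing contrast 93% unadjusted power at 30 minutes.

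**What to change.** Before any unblinded look, amend 10.n as follows:

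1. Name the control as placebo without CBT-I.
2. Add combination minus CBT-I + placebo, on change in TWT, as the test of the combination hypothesis.
3. Test the CBT-I hypothesis with the pooled CBT-I-by-time contrast.
4. State the H1 contrast, pooled or solriamfetol alone versus placebo alone, and number the hypotheses once so that each maps to one contrast.
5. State a multiplicity rule.
6. Reconcile the planned N=20 analysis with the entry that marks interim analysis as not applicable.

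The change is to wording only, with the same data and subjects, but the choices carry costs. Multiplicity control reduces power for the combination test, and items 4 and 5 must be decided together. If H1 is the simple pair, putting it first in a fixed sequence nearly removes the chance of detecting a drug effect seen only with CBT-I (about 5%, against 67% with a pooled H1 and 88% when the combination test is run at 0.025). The pooled CBT-I contrast also loses to a single pair if effects are strongly sub-additive: under 0/30/30/30 the pooled effect is (30 + 0)/2 = 15 minutes, giving 68% against 85%. The protocol calls additivity only a possibility, so the sponsor should weigh this when choosing.

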e. Total Number of Subjects and Sites

40 subjects recruited and completed Phase-1 at one site (Penn).

f. Vulnerable Populations:

The study does not involve any of the following populations:

- Pregnant women
- Fetuses or neonates
- Prisoners
- Children

No subjects, including the economically disadvantaged, employees, and/or students at Penn, will be unduly influenced, encouraged, or coerced into participating in this study. These populations will not be targeted or excluded. IF they are encountered and would like to participate, the appropriate measures will be taken in order to allow them the opportunity to provide consent.

7. Study Intervention (Study drug, device, biologic, vaccine, food etc.)

Solriamfetol, 75mg

a. Description

Solriamfetol (trade name Sunosi), is a norepinephrine-dopamine reuptake inhibitor available in 75mg and 150mg tablets for oral administration during the day. Solriamfetol's primary indication is to treat excessive daytime sleepiness (EDS) in patients diagnosed with OSA or Narcolepsy. It binds to the dopamine transporter and the norepinephrine transporter with affinities (Ki) of 14.2 μ M and 3.7 μ M, respectively), does not undergo significant metabolism in humans, and has a Tmax of ~2 hours (range 1.25–3.0 hours) and a T1/2 of ~7.1 hours. The pharmacokinetic profile of solriamfetol, along with the absence of active metabolites, makes it unlikely that there are accumulation effects with multiple doses over days. See the attachment for a copy of the package insert for solriamfetol.

b. Intervention Regimen

A 2x2 mixed model design. The two factors will be 1) treatment (+/- solriamfetol and +/- CBT-I) and 2) Time (pre-post assessment, with additional follow-up data). Patients with insomnia will be randomly assigned to treatment condition.

c. Receipt

Solriamfetol will be provided (at no cost) by Axsome, and managed by, the Investigational Drug Services of the University of Pennsylvania.

d. Storage

Formulation and storage will be accomplished by Investigational Drug Services of the University of Pennsylvania.

e. Preparation and Packaging

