b. Conflict of Interest

All University of Pennsylvania Investigators will follow the University of Pennsylvania Policy on Conflicts of Interest Related to Research.

c. Subject Stipends or Payments

d. Compensation will be pro-rated for each component of the study for a total of \$500 per participant. Specifically, each participant will receive \$50 for completing the screening visit, \$25 for fully completing baseline sleep diaries, \$200 for fully completing all sleep diaries and questionnaires during the treatment period (8 weeks), \$100 for completing the study, and \$125 for completing the follow-up assessment.

k. Publication Plan

While the primary intent of the study is to garner effect size data, if the inferential statistics are significant with 5-8 subjects per condition, the data will be summarized as a short report for the journal SLEEP or the Journal of Sleep Research.

I. References

Relevant references were placed in text (PMID numbers). Also below.

1: 1. Perlis, M., Jungquist, C., Smith, M. T., & Posner, D. (2005). The cognitive behavioral treatment of insomnia: A treatment manual. Springer. ISBN-10: 0387222529, <https://www.amazon.com/Cognitive-Behavioral-Treatment-Insomnia-Session-ebook/dp/B000PC6BGA>

m. Attachments

- Sample Consent Form

a. Source Documents

The data is being acquired on-line. The original questionnaires are not retained, though they can be regenerated from the database data.

b. Case Report Forms (CRFs)

The data is being acquired on-line. The original questionnaires are not retained, though they can be regenerated from the database data.

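### Section 10.n plans the primary analysis at N=20 while its own item iii says there is no interim analysis, and no level is set; if either look is reportable at .05, the ANOVA's type I error is about 8.6%, not 5%

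*Combined protocol and SAP*

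**What the plan says.** - Section 10.n, main text, on the interim: "An interim unadjusted analysis as per above will be conducted after 50% of the target sample have completed post-treatment (i.e., when N=20". The analysis that this points back to is the 4 x 2 "mixed ANOVA on absolute and percent change in total wake time", followed by a gated step: "If the interaction between condition and time is significant, Dunnett multiple comparisons will be conducted to further investigate differences in TWT". That step sets each active arm against control.
- Section 10.n, item iii, in full: "iii. Interim Analysis N/A".
- Section 10.m gives the only significance level in the document: 10 completers per group, 40 in all, "with 80% power to detect the clinically significant change at an alpha level of .05". It is not divided between looks.
- The section on publication begins as follows: "While the primary intent of the study is to garner effect size data, if the inferential statistics are significant with 5-8 subjects per condition". In that case it calls for a short report.
- Section 11, Stopping Rules, deals with serious adverse events only. The listed contents of the advisory board's six-monthly reports include no efficacy results.
- Section 5 describes the study as double blind.

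**The concern.** The two statements in section 10.n cannot both stand. One commits to running the primary analysis at half the target sample. The other says that no interim analysis applies. Neither gives a level for the look, a reason for it, a rule for acting on it, or a person who sees results by arm in a blinded study.

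The Publication Plan makes this more than an omission. Twenty completers over four conditions is 5 per condition, the lower end of the range at which significance leads to a report. The final target of 10 per condition lies outside that range. So the text can be followed in a way that produces a reported significance test at N=20, with a second test at N=40, both under a single .05.

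Two things would be at stake: the type I error of the primary ANOVA, and the size of an effect reported because it was significant in a very small sample.

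**Working it through.** **Inputs from section 10.m:** 10 per group, four groups, a difference of 30 min, SD 19 min, alpha .05, 80% power. **From section 10.n:** an interim at N=20, taken as 5 per group. **Assumed:** normal data, equal groups, one outcome and one model, two-sided Dunnett (the plan does not state sidedness), and SD 19 for the variable analysed. With two time points, the condition-by-time F test equals a one-way ANOVA on change, which is used below.

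**Step 1: the plan's own figure.** Take two groups 30 min apart and the other two midway (means 0/15/15/30; the pattern is an assumption). The noncentrality is n x sum of squared deviations / SD^2.
- n = 10: 10 x (225 + 0 + 0 + 225) / 361 = 12.47. Against F(3,36), power is 81.1%.
- n = 9: power is 75.8%.

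So 10 per group is the smallest size that gives 80%, and the plan's figure reproduces.

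**Step 2: ANOVA error with two looks.** In 1,000,000 simulated null trials with cumulative data (5 then 10 per group, each look at .05):
- significant at N=40: 0.0498
- significant at N=20: 0.0500
- significant at N=20 but not at N=40: 0.0364
- significant at either: 0.0498 + 0.0364 = 0.0862

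Of the null trials significant at N=20, 0.0364 / 0.0500 = 73% would not be significant at N=40. Simple randomisation with unequal arms gives 8.7%.

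**Step 3: errors after the gated Dunnett** (critical values 2.592 at 16 df and 2.452 at 36 df). True effects are in minutes, in the order control / solriamfetol / CBT-I / combination.

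| False claim counted | True effects | N=40 only | Either look |
|---|---|---|---|
| Any difference from control, either direction | 0/0/0/0 | 3.2% | 5.7% |
| Same | 0/0/30/0 | 3.6% | 6.2% |
| Same (only solriamfetol alone is null) | 0/0/30/30 | 1.9% | 3.4% |
| Benefit only | 0/0/0/0 | 1.6% | 2.9% |
| Benefit only | 0/0/30/0 | 1.8% | 3.1% |
| Solriamfetol alone v control, either direction | 0/0/0/0 | 1.3% | 2.4% |

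**Step 4: power and exaggeration at N=20.** With means 0/15/15/30, the noncentrality at n = 5 is 5 x 450 / 361 = 6.23 and power is 43%. When the N=20 ANOVA is significant, the combination-versus-control difference averages 38.7 min. When the N=40 ANOVA is significant, it averages 32.5 min. The true value is 30. The excess due to selecting at the early look rather than the final one is 38.7 - 32.5 = 6.2 min.

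**The case against.** The strongest reply is that this is a documentation gap, not an error in a test. No section says that the N=20 look is tested at .05, that the trial may stop for efficacy, or that an interim result replaces the final one. The Publication Plan names effect sizes as the main intent. That stands, and it is why every inflation figure here is conditional. It does not remove the contradiction, because the same Publication Plan sentence makes a report depend on significance.

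Four stronger readings are tempting and are not supported.

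- A reader might infer that false treatment claims would exceed 5%. The 5.7% and 6.2% figures count significant worsening as well as benefit. The hypotheses in sections 5.6 and 5.6.2 concern greater improvement, and false claims of benefit reach only 2.9-3.1%. The 6.2% also needs CBT-I to work alone but not with solriamfetol, against the protocol's expectation of possibly additive effects. The 8.6% belongs to the gatekeeping F test, which by itself supports no claim about a treatment.
- A reader might infer repeated testing at 5, 6, 7, 8 and 10 per condition, which would take the ANOVA error to 12.0%. The plan schedules one interim look, at N=20.
- A reader might infer that 5-8 per condition is simply the expected final sample, by taking the 40 in section 6.e as recruits and removing one third for attrition. Section 6.e reads "40 subjects recruited and completed Phase-1 at one site (Penn", so its 40 are completers. The synopsis, section 6 and section 10.m agree, with 60 recruited. The Publication Plan could still have some other short final sample in mind, since it does not mention the interim. That is why the interim result can only be said to be readable as reportable.
- A reader might take the whole gap between 38.7 and 30 min as the cost of the early look. Selection on significance also exaggerates at N=40 (32.5 min). The size depends on the assumed means as well: with 0/0/30/30 the N=20 average is 33.0 min.

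**Conclusion.** The contradiction within section 10.n is certain and needs no assumption. The interim look has no level, purpose, decision rule or recipient, and its link to the Publication Plan is unclear.

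If the look is tested at .05 and either look can be reported, the ANOVA does not hold its 5% (about 8.6%). The effect on treatment claims is smaller and depends on which arms work. Any false difference from control reaches 3.4-6.2%. False claims of benefit reach 2.9-3.1% when all arms are null or only CBT-I alone works. Solriamfetol alone versus control, the comparison closest to the primary hypothesis, roughly doubles but stays at or below 3.4%. If item iii governs, or the look is not inferential, there is no inflation.

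These figures assume normal data, equal groups, two-sided Dunnett, one outcome and one model. The exaggeration figures also rest on means of 0/15/15/30, which are not in the documents. This should be fixed, and preferably before 20 subjects complete post-treatment.

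**What to change.** Make section 10.n, item iii and the Publication Plan agree.

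**Preferred.** State in 10.n and item iii that the N=20 look is not inferential. It can be pooled and blinded (recruitment, attrition, pooled SD), or estimation only, with no p-value and no efficacy claim. If results by arm are produced, name who sees them. Keep the single .05 test at N=40. In the Publication Plan, say what 5-8 per condition refers to, and remove reporting that depends on significance there. The cost is wording in three places and the loss of an early significance report. A blinded look also gives up interim effect estimates. The N=40 test keeps its power.

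**Alternative, if an inferential look is wanted.** Replace item iii with prespecified levels that total 5%, for example 0.005 at N=20 and 0.047 at N=40. Run Dunnett at the level of each look, and name the N=40 estimate as the primary result even if an early report appears. In simulation the ANOVA error is then 5.0%. With means 0/15/15/30, power is 80.5% instead of 81.1%. The early boundary is crossed in about 12% of trials, and the combination difference in those averages about 44.8 min at N=20 against a true 30, so early reports become rarer but more exaggerated. Other splits also work, such as about .028 at each look.

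These levels cover one outcome and one model. Section 10.n tests absolute and percent change and says "These analyses will be unadjusted in the first instance and then adjusted for covariates (primarily, age and sex", so one outcome and one model would have to be named primary.
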